APPENDIX 2: MGH- FAST ADDITIVE SUMMARY OF TREATMENT

FAST: Fast Additive Summary of Treatment

Please complete the row for every treatment you tried. If you're not sure, use your best guess.

	a) Longest duration?	b) Benefit?	c) Why stopped?	d) Missed doses?
	less than 4 weeks	4-8 weeks	8 weeks - 6 months	> 6 months
	Back to normal	Better but not well	A bit/None (Still treated) Side effects	Lack of benefit Cost/other
	once a week or less	2+ times a week		Highest dose?
Mood stabilizers				
Lithobid, eskalith	Lithium carb/citrate			
Depakote, depakene	Valproate			
Equetro, Tegretol	Carbamazepine			
Lamictal	Lamotrigine			
At the same time : any two of the above				
Antipsychotics (including injected/shots)				
Zyprexa	Olanzapine			
Clozaril	Clozapine			
Risperdal	Risperidone			
Seroquel	Quetiapine			
Abilify	Aripiprazole			
Geodon	Ziprasidone			
Saphris	Asenapine			
Latuda	Lurasidone			
Invega	Paliperidone			
Prolixin	Fluphenazine			
Haldol	Haloperidol			
Orap	Pimozide			
Stelazine	Trifluoperazine			
Loxitane	Loxapine			
Molindone	Moban			
Trilafon	Perphenazine			
Navane	Tiotixene			
Thorazine	Chlorpromazine			
Serentil	Mesoridazine			
Mellaril	Thioridazine			
Other:				
Any weekly or monthly injection				
At the same time : Clozapine and another				
At the same time : Two antipsychotics				

FAST: Fast Additive Summary of Treatment

Please complete the row for every treatment you tried. If you're not sure, use your best guess.

		a) Longest duration?	b) Benefit?	c) Why stopped?	d) Missed doses?
		less than 4 weeks 4-8 weeks 8 weeks - 6 months > 6 months	Back to normal Better but not well	A bit/None (Still treated) Side effects Lack of benefit Cost/other	once a week or less 2+ times a week Highest dose?
Antidepressants (rate the longest trial)					
Prazac	Fluoxetine				
Paxil	Paroxetine				
Zoloft	Sertraline				
Celexa	Citalopram				
Lexapro	Escitalopram				
Luvox	Fluvoxamine				
Effexor	Venlafaxine				
Cymbalta	Duloxetine				
Wellbutrin	Bupropion, budeprion				
Remeron	Mirtazapine				
Viibryd	Vilazodone				
Brintellix	Vortioxetine				
Tofranil	Imipramine				
Pamelor	Nortriptyline				
Anafranil	Clomipramine				
Elavil	Amitriptyline				
Vivactil	Protriptyline				
Surmontil	Trimipramine				
Parnate	Tranycypramine				
Nardil	Phenelzine				
Emsam	Selegiline				
At the same time : Two of the above					
Electroconvulsive therapy (ECT)					
Cognitive-behavioral therapy (CBT)					
Other depression medicines					
SAM-e	S-adenylmethionine				
Provigil/nuvigil	Modafinil/armodafinil				
Mirapex	Pramipexole				
Requip	Ropinirole				
Deplin	Methylfolate				
Dexedrine	Dextroamphetamine				
Ritalin, concerta	Methylphenidate				
Adderall	Amphetamine salts				
Buspar	Buspirone				
Synthroid	Thyroid hormone				

Atypical Antipsychotic Drugs

Aripiprazole (marketed as Abilify)

Asenapine Maleate (marketed as Saphris)

Clozapine (marketed as Clozaril)

Iloperidone (marketed as Fanapt)

Lurasidone (marketed as Latuda)

Olanzapine (marketed as Zyprexa)

Olanzapine/Fluoxetine (marketed as Symbyax)

Paliperidone (marketed as Invega)

Quetiapine (marketed as Seroquel)

Risperidone (marketed as Risperdal)

Ziprasidone (marketed as Geodon)

Source: <http://www.fda.gov/drugs/drugsafety/ucm243903.htm#list>

APPENDIX 3: CONCOMITANT MEDICATIONS ALLOWED

Drug Name or Class	Episodic Use (prn)	Chronic Use	Restrictions/Comment
Analgesics	Y	Y	Non-narcotic analgesics are allowed. Medically appropriate episodic use of narcotic analgesics is allowed for acute medical indications but is limited to no more than 3 days for each episode. Chronic NSAID use is allowed; tramadol is not allowed.
Anesthetics, general	Y	—	If procedures requiring general anesthesia are to occur/have occurred, please contact MGH CTNI to report the medical condition(s).
Anesthetics, local	Y	N	—
Anorexics	N	N	—
Antacids	Y	Y	—
Antiacne	Y	Y	Topical agents only, including topical antibiotics. Isotretinoin (Accutane) is not allowed.
Antiangular agents	N	N	—
Antiarrhythmics	N	N	—
Antiasthma agents	Y	Y	—
Antibiotics	Y	Y	Chronic use of topical or oral antibiotics for acne is allowed, with the exception of the MAOI linezolid (Zyvox) and isoniazid, which are not allowed. Erythromycin, clarithromycin, rifampin are excluded.
Anticoagulants	N	N	Warfarin (Coumadin) is not allowed. Antiplatelet agents are allowed (see "Antiplatelets").
Anticholinergics	Y	Y	Except for scopolamine.
Anticonvulsants	N	YY	Gabapentin and pregabalin are allowed. Other anticonvulsants are not allowed, including lamotrigine and carbamazepine.
Antidepressants	N	Y	Stable (for at least 4 weeks prior to screening), ongoing antidepressant therapy is required during the course of the study. No dose changes are allowed during the study. Monoamine oxidase inhibitors (which may have unknown drug-drug interactions) are excluded. Concomitant use of trazodone (up to 200mg daily) is allowed. Nefazodone is excluded.

Antidiarrheal preparations	Y	N	Only loperamide HCl (Imodium), bismuth subsalicylate (Pepto-Bismol), and kaolin preparations are allowed.
Antifungals, systemic	N	Y	—
Antifungals, topical	Y	Y	Ketoconazole and itraconazole are excluded
Antihistamines	Y	Y	The use of combinations containing pseudoephedrine or phenylephrine is not allowed. Combination products containing the word nighttime or some synonym routinely include a sedating antihistamine and are not allowed. Combination products ending in “-D” routinely contain a stimulant such as phenylephrine, and the appropriate limits above apply to them.
Anti-hypertensives	N	Y	Diltiazem, verapamil are excluded
Anti-impotence medications	N	N	—
Anti-inflammatory drugs	Y	Y ^a	Indomethacin (Indocin) and systemic corticosteroids are not allowed.
Antifungal	Y	Y	Itraconazole is excluded
Antimigraine	Y	Y	Triptans are not allowed
Antinauseants/Antiemetics	Y	N	Phosphoric acid preparations (Emetrol, Emecheck), bismuth subsalicylate (Pepto-Bismol), cola syrup, 5-HT ₃ receptor antagonists (e.g., ondansetron), and prokinetic agents (metoclopramide) are allowed. Scopolamine is not allowed (see section on antihistamines).
Antineoplastics/Immunosuppressant agents	N	Y ^c	Interferons, methotrexate, and other immunosuppressant agents are not allowed. Call MGH CTNI for approval for certain cases in cancer remission maintaining therapy.
Antiobesity/Appetite suppressants	N	N	OTC Alli (Xenical), sibutramine (Meridia), and phentermine (Adipex-P and others) are not allowed.
Antiplatelet agents	N	Y ^b	Aspirin (maximum 325 mg/day) and clopidogrel (Plavix) are allowed.
Antipsoriatic treatments	Y	Y	Only topical agents are allowed. Acitretin (Soriatane) is not allowed.
Antipsychotics	N	Y	Stable in dosing at least 8 weeks prior to randomization is allowed.

Antismoking medications	N	Y ^c	Varenicline (Chantix) is not allowed. Chronic nicotine replacement may be allowed in certain cases after review with MGH CTNI.
Antiviral agents	Y	Y	Only oral or topical agents are allowed. Only acyclovir, famciclovir, valacyclovir, penciclovir, docosanol, trifluridine, and vidarabine are allowed. Amantadine, rimantadine, indinavir, nelfinavir, ritonavir, saquinavir are not allowed. Tamiflu (oseltamivir phosphate), and Relenza (zanamivir) inhalants are permitted for influenza prophylaxis but use is limited to a 7- to 14-day course in accordance with prescribing information. Interferons are not allowed.
Anxiolytics	Y	Y	Chronic, stable treatment with benzodiazepines for reasons other than sleep is allowed. Stable dosing at least four weeks prior to randomization is required for sleep agents. Up to 1mg of benzodiazepine in a 24h period can be utilized as needed during the study period.
Benign prostatic hyperplasia treatments	N	Y ^b	Male patients who have symptoms of obstructed voiding should not be included in the study. Surgically or medically treated patients must be asymptomatic and receiving a stable dosage of allowed medications (α -1 blockers, finasteride, or dutasteride) for 1 month before screening.
Buspirone	N	Y	Stable in dosing at least four weeks prior to randomization is allowed.
Cough/cold preparations	Y	N	Use of cough and cold preparations containing pseudoephedrine or dextromethorphan is not allowed, as are those containing phenylephrine. Combination products ending in “-D” routinely contain a stimulant such as phenylephrine, and the appropriate limits apply to them. (See “Antihistamines”.)
Diuretics	Y	Y ^b	Episodic use of diuretics is restricted to treatment of premenstrual symptoms. For chronic use, medication and dosage should be stable for 1 month before screening.
Dopaminergics	N	Y	Dopamine agonists for restless leg syndrome are allowed. Stable in dosing at least four weeks prior to randomization is allowed.

Gastrointestinal:			
• H2-blockers/ • proton pump inhibitors/ • prokinetic agents	Y	Y	Cimetidine (Tagamet) is not allowed. Metoclopramide is not allowed.
Hormonal (noncontraceptive) therapies	N	Y	See below.
Hormone suppressants	N	Y ^b	Only finasteride (Proscar) and dutasteride (Avodart) are allowed.
Hormones: reproductive	N	Y	Systemic hormonal contraceptives (oral contraceptives of estrogen and progestin combinations, depot injections such as Depo-Provera, the contraceptive implant Implanon, or transdermally delivered contraceptives such as Ortho Evra) are allowed
Hormones: thyroid	N	Y	Thyroid hormone replacement is allowed (dosage of thyroid medication should be stable for 3 months before screening). Therapeutic use for psychiatric disorders (e.g., T3 augmentation) is not allowed
Hypoglycemic agents	N	Y	Oral hypoglycemic agents are allowed. Insulin is not allowed
Hypolipidemics	N	Y ^b	Ezetimibe (Zetia) is allowed
Hypolipidemics: bile acid sequestrants	N	N	—
Hypolipidemics: fibrates	N	Y ^b	Gemfibrozil and fenofibrate are allowed
Hypolipidemics: niacin	N	N	Niacin and niacinamide are not allowed
Hypolipidemics: statins	N	Y ^b	Lovastatin, simvastatin, pravastatin, atorvastatin, fluvastatin, and rosuvastatin are allowed
Laxatives	Y	Y ^a	Only fiber-based products and docusate sodium (Colace) are allowed
Lithium	N	Y	Stable dosing at least four weeks prior to randomization is allowed.

Medications that are primarily metabolized by CYP2C8 (e.g., cerivastatin, paclitaxel, repaglinide, sorafenib, and torsemide)	N	N	—
Muscle relaxants	N	N	—
NMDA receptor antagonist	N	N	Memantine is excluded.
Opioid agonists/analgesics (e.g., codeine, hydrocodone, methadone, morphine, maperidine, propoxyphene) and antagonists (e.g., naltrexone, naloxone, nalmefene)	N*	N*	See section on analgesics for exceptions
Proton pump inhibitors or H2 receptor blockers	Y	Y	—
Sedatives/hypnotics	N	Y	Ongoing, stable hypnotic therapy (e.g., zolpidem, zaleplon, benzodiazepine hypnotics, and low-dose trazodone 50-200mg) will be allowed during the course of the study. Eszopiclone is not allowed.
Steroids/systemic	Y	N	Systemic steroid treatment will be allowed only for medical emergencies, such as severe allergic reactions
Steroids/topical and inhalant	Y	Y	—
Steroids/intra-articular	Y	NA	—
Stimulants	N	N	Oral or transdermal methylphenidate, amphetamine products or prodrugs, pseudoephedrine, modafinil (Provigil), and other medications of same category are not allowed
Vaccines	Y	NA	—

- a If being taken prior to enrolling in the study.
- b If being taken for at least 3 months prior to enrolling in the study and the dose has been stable for at least 1 month.
- c If approved by MGH CTNI Medical Monitor5-HT₃ = 5-hydroxytryptamine receptor type 3; 5-HTP = 5-hydroxytryptophan; ACE = angiotensin-converting enzyme; CR = controlled release; DHEA = dehydroepiandrosterone; N = no; NA = not applicable; OTC = over the counter; PRN = as needed (prorenataT3prorenataT3=triiodothyronine; Y = yes.

APPENDIX 5: STUDY SCALES

The Positive and Negative Syndrome Scale (PANSS)

Link: <http://www.emotionalwellbeing.southcentral.npanss-positive-and-negative-syndrome-scale-pdf-document>.

Clinical Global Impressions–Severity (CGI-S) and Clinical Global Impressions–Improvement (CGI-I) Scales

Link: <http://miksa.ils.unc.edu/unc-hit/media/CGI.pdf>

Abnormal Involuntary Movement Scale (AIMS)

Link: <http://www.atlantapsychiatry.com/forms/AIMS.pdf>

Systematic Assessment for Treatment Emergent Effects–Systematic Inquiry (SAFTEE-SI)

Link: <https://www.cognitiongroup.com/pdf/aims.pdf>

Columbia-Suicide Severity Rating Scale (C-SSRS)

Link: http://cssrs.columbia.edu/docs/C-SSRS_1_14_09_Baseline.pdf

The Measurement and Treatment Research to Improve Cognition in Schizophrenia (MATRICS) Consensus Cognitive Battery (MCCB)

Link: MATRICS Consensus Cognitive Battery (MCCB)

The University of California San Diego (UCSD) Performance-based Skills Assessment Brief (UPSA-B)

http://www.researchgate.net/UPSA_B

## DATA ANALYSIS

This section presents general information about statistical considerations and concepts such as randomization, stratification, statistical power, sample size, and a brief discussion on analysis methodology.

### Treatment Groups

The following treatment groups will be assessed:

Table 4. Study Treatments

Group	Description
Test Treatment	Sodium Nitroprusside (0.5 µg/kg/min for 4 hours)
Control Treatment	Placebo (5% dextrose for 4 hours)

### Description of Study Endpoints

#### Primary Efficacy Endpoint

- Mean change from baseline in Positive and Negative Syndrome Scale (PANSS) total score after 2 weeks of randomized treatment using SPCD.

#### Secondary Efficacy Endpoints

- Percent change from baseline in the PANSS total score after 2 weeks of treatment using SPCD
- Percentage of subjects with 20% or more reduction from baseline in PANSS total score after 2 weeks of treatment using SPCD
- Percent change in PANSS subscales using SPCD

#### Additional Efficacy Endpoints

- Percent change in Clinical Global Impression-Severity (CGI-S) using SPCD
- Percent change in MATRICS Consensus Cognitive Battery (MCCB) using SPCD

#### Safety Assessments

- Incidence of Treatment-Emergent Adverse Events (TEAE)

- Incidence of withdrawals from the study due to TEAEs
- Percent change in Abnormal Involuntary Movement Scale (AIMS)
- Percent change in Systematic Assessment for Treatment Emergent Effects–Systematic Inquiry (SAFTEE-SI)
- Assessment of suicidality per the Columbia-Suicide Severity Rating Scale (C-SSRS)
- Changes in blood pressure and heart rate
- Changes in electrocardiogram (ECG) parameters

## **Sample Size Determination and Rationale**

Sixty (60) subjects will be randomized in an effort to assure that 48 subjects complete the study.

The RCT Logic Calculator (by Schoenfeld, D and Ivanova,A; <http://www.rctlogic.com/calculator/calculator-continuous.aspx>) was used for this sample size calculation. This sample size will provide “sufficient” statistical power for the selected primary endpoint. The sample size calculation is based on the assumption that there is a clinically meaningful weighted (50%) average difference of 10 points (9 points in Stage 1 and 11 points in Stage 2) between sodium nitroprusside and placebo group accordingly, (with standard deviation of 14) in PANSS total scores after 2 weeks of treatment between the two treatment groups. This power calculation is based on a 20% attrition by Week 4 and 30% placebo response at the end of Stage 1. Under the above assumptions, 60 subjects will be required to meet the Type I error rate of 0.05 and an 81% power.

## **Randomization**

This is a double-blind, placebo-controlled, multi-center, randomized clinical trial. Subjects who have provided written informed consent and have met all the inclusion criteria and have met none of the exclusion criteria will be randomized to one of the three treatment sequences.

The study design contains two double-blind treatment phases (i.e. Phase 1 and Phase 2) of the same duration of two weeks. Subjects will be randomly assigned using stratified block randomization. The randomization scheme will be programmed in to the CTMS software and will generate a randomization code for each subject upon enrollment into the study. Subjects will be stratified by primary treatment status (clozapine, versus antipsychotic other than clozapine) and by site. The number of subjects taking clozapine will be restricted to 20 study wide.

## **Blinding and prevention of Bias**

All subjects, Investigators and their staff involved in the management of the study will be blinded to treatment assignments.

Treatment unblinding for the study will occur after all clinical data have been received, data inconsistencies have been resolved, and the database is locked, except for safety reasons on a case by case basis (i.e., emergency unblinding).

## **Interim Analysis**

There will be no interim analysis for this trial.

## **General Statistical Considerations**

All collected study data will be presented in subject data listings. Statistical analyses will be performed using SAS® for Windows, version 9.3 or later. Descriptive statistics (n, mean, standard deviation, median, minimum and maximum) will be calculated by treatment group for continuous variables. Frequencies and percentages will be presented by treatment group for categorical variables.

## **Analysis Populations**

The details of the analysis population to be used for the study are described in the below sections. All the subjects who were randomized in the study will be considered for analysis. For the primary and secondary endpoint analyses the following set of subject will be accounted:

- All subjects randomized to the sodium nitroprusside group in Phase 1 of the study (~ 20 subjects)
- All subjects randomized to the Placebo group in Phase 1 of the study (~ 40 subjects)
- All subjects who did not respond to placebo in Phase 1 and were pre-randomized to the sodium nitroprusside group in Phase 2 of the study (~11 subjects)
- All subjects who did not respond to placebo in Phase 1 and were pre-randomized to the placebo group in Phase 2 of the study (~11 subjects)

## **Intent-to-Treat (ITT) population**

The Intent-to-Treat (ITT) population is defined as all randomized subjects. The ITT population will be the primary population for the analysis of the primary, secondary, and additional efficacy endpoints.

## **Per Protocol (PP) Population**

The Per Protocol (PP) population is defined as all randomized subjects who were not associated with a major protocol violation. This population will be identified before the database lock. The PP analysis of primary, secondary and additional endpoints will be considered supportive.

## **Safety Population**

The Safety population is defined as any subject receiving the treatment after randomization. This population will be used for the analysis of safety parameters.

### **Covariates**

For efficacy analyses, baseline values will be used as covariates in the analysis models.

### ***Missing data***

For efficacy evaluation data points missing data will be imputed per the method that will be detailed in the SAP for the study.

### ***Multiple Comparisons and Multiplicity***

This is a two phase Sequential Parallel Comparison Design (SPCD) study.

A two-stage test (Weighted Z-test approach with fixed weight of 0.5 for each part of the study) will be used to combine the data on treatment effects from the two stages of the study. This method will address the Type I error rate adjustment to protect the trial wise Type I error at the final analysis.

For the primary endpoint there will be only one hypothesis testing and there will be no Type I error adjustment for testing this endpoint.

There will also be no Type I error adjustment on the hypotheses testing of the secondary endpoints, other than using the Closed Test procedure.

## **Statistical Methods**

A Statistical Analysis Plan (SAP) will be developed and approved before the database is locked. The SAP will present the detailed statistical methodology to be used in analyzing the efficacy and safety data from this trial. Inferential statistics for all inferential statistical analysis will be based on a 2 sided test with Type I Error rate of 0.05.

All the efficacy endpoints presented here will be conducted using both the evaluable and ITT populations. All safety analysis will be conducted using the safety population.

All data collected will be summarized according to the variable type:

- Continuous data summaries will include:
  - Number of observations, mean, standard deviation, median, and minimum and maximum values.
  - Analysis of Covariance using the stratification factor for inferential statistics.
- Categorical data summaries will include:
  - Frequency counts and percentages.
  - Logit model will be used for inferential statistics using the stratification factors referenced.

## **Subject Disposition**

The disposition of all subjects who sign an ICF will be provided. The numbers of subjects screened, randomized, re-randomized, completed, and discontinued during the study, as well as the reasons for all post-randomization discontinuations will be summarized by treatment group. Disposition and reason for study discontinuation will also be provided as a by-subject listing.

## **Demographics and baseline characteristics analysis**

Demographics and baseline characteristics will be summarized by treatment group using appropriate descriptive statistics.

## **Concomitant Medications**

Concomitant medications will be summarized separately for the Safety population. All prior and concomitant medications recorded in the case report form will be coded to all matching Anatomic Therapeutic Classification codes using the most recent version of WHO Drug version. Descriptive summaries, by treatment group and stage of the study, will be prepared using the coded term. All concomitant medications recorded in the case report form will be listed.

## **Efficacy Analyses**

### **Primary Efficacy Analyses**

Primary Analysis of the primary, secondary and additional efficacy endpoints will be conducted on the ITT population using SPCD.

- Primary Endpoint: Mixed Model Repeated Measures analysis (MMRM)/non-parametric methods will be used to compare using SPCD the difference between the two treatment groups on the primary endpoint depending on the distribution of the data. A weight of 50% will be used in pooling the data from Stages 1 and 2.
- Secondary Endpoints: To maintain the trial-wise Type I error rate at 0.05, a closed test procedure will be used for the secondary endpoints. The order of the endpoints will be pre-specified in the statistical analysis plan prior to database lock. A weight of 50% will be used in pooling the data from Stages 1 and 2, using SPCD.
  - Continuous data comparisons will be based on Mixed Model Repeated Measures (MMRM), if the Normality assumption is met, or a rank –ANCOVA analysis i.e., an ANCOVA analysis on rank-transformed data will be used if the data is not normally distributed.
  - Categorical data comparisons will be based on Logit model.
- Additional Efficacy Endpoints: These endpoints are considered exploratory endpoints. These additional Efficacy Endpoints will be analyzed using the similar methods outlined for the primary and secondary endpoints or additional appropriate methods, if needed. The statistical methods will be detailed in the SAP.

## **Supportive Analysis**

To assess the consistency of the Primary Analysis results, supportive analysis will be conducted using the PP population. Statistical methodology for the supportive analyses will be the same as that of the primary analysis, with the exception of the analysis population used. The PP population will be used for the supportive analysis while the ITT population will be used for the primary analysis.

## **Safety Analyses**

### Adverse Events

Adverse events will be coded using MedDRA. Treatment Emergent AE's (TEAE) are defined as events with an onset on or after the first randomized treatment. TEAEs will be summarized by treatment group and by stage of the study, System Organ Class, and preferred term. The following TEAE summaries will be provided:

- TEAEs by severity grade
- TEAEs by relationship to study treatment.

In addition, separate summaries of serious adverse events, and adverse events resulting in discontinuation of study treatment will be presented.

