In accordance with International Conference on Harmonization (ICH) and Food and Drug Administration (FDA) guidance, any study related event incurred by a subject that occurs after the first study-related procedure to the completion of the protocol-defined safety surveillance period, that represents a change (positive or negative) in frequency or severity from a baseline (pre-study) event (if any), regardless of the presence of causal relationship or medical significance, is a reportable AE.

Abnormal results of diagnostic procedures, including laboratory test abnormalities, are considered AEs if they:

- Result in discontinuation from the study,
- Require treatment or any other therapeutic intervention,

- Require further diagnostic evaluation (excluding a repetition of the same procedure to confirm the abnormality), or
- Are associated with clinical signs or symptoms that would have a significant clinical impact, as determined by the PI.

Performing Adverse Events Assessments

The PI is ultimately responsible for assessing and reporting all adverse events as outlined in the protocol. The assessment of AEs may be delegated to a medically qualified Sub-Investigator, trained on this study protocol, who is listed on the FDA Form 1572 or equivalent document, and on the delegation of authority form.

AEs should be volunteered by the subject, or solicited from the subjects using a standard statement, from examination of the subject at a clinic visit, or from observations of clinically significant lab values or special exam abnormal values. AEs will not be solicited by the use of a specific list of anticipated events.

All AEs are to be assessed and recorded in a timely manner and followed to resolution or until the Investigator determines that there is not an anticipated resolution. Each AE is to be documented with reference to severity, date of occurrence, duration, treatment, and outcome. Furthermore, each AE is to be classified as being serious or non-serious (as per definitions). In addition, the PI or delegated medically qualified Sub-Investigator must assess whether the AE is drug-related or not. Changes in severity of AEs and resolution dates should be documented as separate events.

Timing

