AEs will be captured from the first study-related procedure through to the completion of the protocol defined safety surveillance period. For the purposes of this study, the period of observation for collection of AEs extends from the time the subject gives informed consent until the final visit.

Surgical procedures, planned before enrollment of the subject in the study, are not considered AEs if the condition was known before study inclusion. In this case the medical condition should be reported in the subject's medical history. Intermittent adverse events will not be reported as multiple adverse events. The definition of an intermittent adverse event is "a recurring event of consistent severity, frequency, and causality."

Severity

Each AE is to be documented with reference to severity. Changes in severity of AEs and resolution dates should be documented as separate events. Any event that ameliorates over more than one assessment time point may be considered for listing as a single event at the highest severity.

Table 2. Definition of Intensity of Adverse Events

Intensity	Definition
Mild	Causes transient or mild discomfort; no limitation of usual activities; no medical intervention required.
Moderate	Causes mild to moderate limitation in activity; some limitation of usual activities; no or minimal medical intervention or therapy is required.
Severe	Causes marked limitation in activity; some assistance is usually required; medical intervention or therapy is required; hospitalization is probable.

The term “severe” is often used to describe the intensity (severity) of a specific event (as in mild, moderate, or severe); the event itself, however, may be of relatively minor medical significance (such as a severe headache). This is not the same as “serious,” which is based on subject/event outcome or action criteria usually associated with events that pose a threat to a subject’s life or functioning. Seriousness (not severity) serves as a guide for defining regulatory reporting obligations.

Relationship

The PI or a medically qualified Sub-Investigator, trained on this study protocol, listed on the 1572 or equivalent document and on the delegation of authority form, is responsible for determining the adverse event relationship to the investigational product.

The following categories will be used to define the relationship of an AE to the administration of the IMP:

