In the event of a SAE, the PI or designate will notify the MGH-CTNI Medical Monitor by phone or email within 24 hours of the event and will email supporting documentation

within 48 hours of the event and then as relevant data is available within the following week.

The PI must inform the IRB immediately regarding any AE (does not have to be causally related) that is both serious and unexpected; or that represents a series of AEs that, on analysis, is unanticipated, or occurs at an unanticipated frequency, or otherwise represents an unanticipated safety risk to the study subject. The IRB may subsequently choose to modify the informed consent or request changes to the protocol.

Treatment-Emergent Adverse Events

A treatment emergent adverse event (TEAE) is an AE that either began following initiation of study treatment or was present prior to the initiation of the treatment, but increased in frequency or severity following initiation treatment, regardless of causality.

All TEAEs (post infusion) will be captured on the subject source documents for all required assessments and data transferred to the eCRF. The reporting PI or medically qualified Sub-Investigator will sign and date the source document and eCRF.

Procedures and follow-up of Subjects Experiencing AEs after Completion of or Withdrawal from the Study

If a subject experiences the onset of a SAE within a period of 30 days following study completion and, in the opinion of the PI or medically qualified Sub-Investigator, it is associated with the study, it will be followed up and reported as described above.

Protocol Waivers and Violations

Protocol Waivers

Protocol waivers will be assessed on a case by case basis by the medical monitor and the principle investigator for this study.

Procedure for Non-Compliant Subjects

Subjects who miss a study visit will be allowed (at the discretion of the PI) to make up that visit the next day. Subjects who miss more than one visit will be discontinued from the study. Subjects who withdraw consent will no longer have data collected for the study. Every effort will be made to maintain contact with patients who are discontinued, but who do not withdraw consent, according to the study schedule for 30 days post-treatment in order to collect safety data.

Protocol Deviation and Violation Definitions

Protocol violations as defined in the table below will be reported as described in the Manual of Operations.

Table 3. Major and Minor Protocol Violations

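### Treatment-emergent adverse events are defined in two incompatible ways, so some events that start before the first infusion and worsen after it can be missed from the TEAE tables

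*SAP*

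**What the plan says.** Three places define a TEAE.

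- SAP, Safety Analyses, Adverse Events: "Treatment Emergent AE's (TEAE) are defined as events with an onset on or after the first randomized treatment". Nothing in the SAP adds worsening.
- Protocol Section M, Safety Analyses, Adverse Events: the same onset-only sentence.
- Protocol Section H, Treatment-Emergent Adverse Events: an event that began after treatment started, or one that "was present prior to the initiation of the treatment, but increased in frequency or severity following initiation treatment, regardless of causality".

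The recording rules are in Protocol Section H, Evaluation of Adverse Events:

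- Timing: "the period of observation for collection of AEs extends from the time the subject gives informed consent until the final visit".
- Performing Adverse Events Assessments, repeated under Severity: "Changes in severity of AEs and resolution dates should be documented as separate events".
- Severity, the next sentence: an event that improves over more than one assessment "may be considered for listing as a single event at the highest severity".
- Timing: "Intermittent adverse events will not be reported as multiple adverse events". An intermittent event is one that recurs with unchanged severity, frequency and causality.

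TEAE incidence is the first item under Safety Assessments in the SAP. TEAE tables are planned by treatment group and stage, by system organ class and preferred term, by severity and by relationship.

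**The concern.** The programmer has two rules for one endpoint, and they disagree about an adverse event that is already present at the first infusion and then gets worse. Such events are possible. Consent is taken at Visit 1 (Day -28 to -14) and the first infusion is on Day 0, which leaves about two to four weeks in which adverse events are logged before any treatment. SAFTEE-SI is completed at Visit 3, before the infusion, and the study physician decides whether its moderate and severe items become adverse events. During the infusion, staff watch for headache, nausea and dizziness, which a subject may also have had beforehand.

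An onset-only rule, applied to an entry that keeps its pre-infusion date, leaves the worsening out of TEAE incidence. The error in the overall count runs one way: leaving out worsened events can lower it but not raise it.

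**Working it through.** No arithmetic applies; the documents give no adverse event rates. The check is to take each type of event through both definitions under the protocol's own recording rules.

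| Event | Section H definition | Section M and SAP definition |
|---|---|---|
| (a) Starts after the first infusion | TEAE | TEAE |
| (b) Pre-study condition that worsens after infusion | TEAE | TEAE if onset is dated at the worsening; Section H (Evaluation of Adverse Events, Definition) makes the change a reportable event |
| (c) Logged between consent and infusion; severity rises after infusion | TEAE | TEAE if the separate entry carries the date of the change; lost if the first onset date is kept or the entry is not split |
| (d) Logged between consent and infusion; only frequency rises after infusion | TEAE | Lost unless the site opens a new entry |
| (e) Logged before infusion, peaks after it, then fades, and is listed once at its worst | TEAE | Lost if the single line keeps its first onset date |

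For (c), the separate-entry rule is stated twice, so a split is expected. Neither statement says which onset date the new entry takes.

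For (d), the separate-entry rule names severity and resolution dates, not frequency. An event whose frequency rises no longer meets the definition of an intermittent event, so the ban on multiple reporting stops applying to it. That permits a second entry; it does not require one.

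For (e), the single-line option is discretionary, so sites may differ, and it does not address dates.

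**Outputs affected.** These are TEAE incidence and the TEAE tables. The SAP describes the summaries of serious events and of events leading to treatment discontinuation in terms of adverse events, not TEAEs, and General Statistical Considerations has all collected data listed. Those outputs do not depend on the TEAE definition.

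**Stage.** Take one of the 20 subjects planned for placebo-drug. An event starts in Phase 1 on placebo and worsens after the Day 14 drug infusion. It is a TEAE under either definition, because both look back to the start of study treatment. If the entry is not split, tabulation by first onset puts it under placebo in Phase 1, and the worsening on drug does not appear under drug in Phase 2. Neither definition says how to assign it.

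**The case against.** A reader might infer that the SAP departs from the protocol. It does not simply do so: it repeats the protocol's own analysis section, and the contradiction lies inside the protocol, between Sections H and M. Changing the SAP alone would leave Section M uncorrected and set the two documents against each other.

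A reader might also infer that every worsened event is lost. The documents do not support that. Severity increases are to be entered separately, and those dated at the change are counted. Worsening of a pre-study condition is reportable in its own right. Section H also asks for all post-infusion TEAEs to be captured in the source documents and eCRF, directly beneath the definition that includes worsening. The single-line option reads most naturally as sparing sites from logging each step of an improvement; using it to join a pre-infusion event to a post-infusion peak is possible but not its evident purpose.

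Nor does the plan lose such events from safety reporting as a whole. The serious-event and discontinuation summaries and the listings remain, and SAFTEE-SI, AIMS, vital signs and ECG are reported separately. The same definition applies to both treatments, the TEAE summaries are descriptive, and no efficacy result changes.

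All of this stands and limits the point. It does not remove the two definitions, the missing date rule, the lack of an explicit rule for frequency or the open question of stage.

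**Conclusion.** The conflict between the definitions is certain from the text. Its effect is conditional: it reaches only events that start between consent and the first infusion and then worsen without a new entry dated at the change, chiefly frequency-only increases and events kept on one line. The Phase 1 event that worsens after Day 14 is a separate question of attribution.

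The number of events cannot be estimated from the documents and is probably small. The definition can only lower the overall TEAE count. Whether it would distort the comparison of drug with placebo is unknown: that depends on whether worsening is more common on one treatment, for which no rates are given. This is a low-severity point, worth correcting because it concerns a named safety endpoint and the correction is cheap.

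**What to change.** Use one TEAE definition in Protocol Section H, Protocol Section M and the SAP: an adverse event that starts, or becomes more frequent or more severe, after the first infusion. Add two rules:

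- A worsened event, whether in severity or in frequency, takes the date of the change as its onset. The single-line option then cannot join a pre-infusion entry to a post-infusion worsening.
- It is tabulated under the stage and treatment in which it worsened, so a worsening after the Day 14 infusion in the placebo-drug sequence is counted under drug in Phase 2.

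The cost is about one sentence in each document and a programming flag, set before database lock. No new assessment is needed. For any event already held on one line, the date of the change would have to be taken from the source documents.
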